Out-of-pocket pharmacy costs will be analyzed descriptively before and after high-dose U-500R syringe initiation, high-dose U-500R Kwikpen initiation, and any high-dose U-500R initiation. Numbers and percentages will be provided for dichotomous and polychotomous variables. Means and SDs, along with the median, minimum and maximum will be provided for continuous variables. To determine the statistical significance of before and after values, McNemar's test will be used for categorical variables, and the paired t-test will be used for continuous variables.

Multivariate Analysis

A generalized linear mixed model (details above) with log link will be used to evaluate factors associated with insulin-related out-of-pocket pharmacy costs in the pre-and post-index periods among high-dose U-500R syringe initiators, high-dose U-500R Kwikpen initiators, and any high-dose U-500R initiation. For this objective, the mixed linear model will help to evaluate the effect of both time-varying and time-independent variables on the costs, while taking into account for correlation due to multiple assessments from the same individual. In the current model, costs (measured at 2 time intervals [before and after the index event; U-500R initiation]) will be designated as the dependent variable. Observed TDD will be designated as the time-varying covariate in the model (measured both before and after the index date), and the time-independent covariates will include the demographic and clinical characteristics.

The complete list of covariates will include:

- age;
- sex;
- region;
- pre-index CCI score;
- observed TDD from claims ;
- Medicare (yes/no); and
- time (pre/post).

[2019-8636] Observational Study Protocol

[figure not shown]
Note:

- ❖ Age, sex, region, Medicare (yes/no), and CCI score will be assessed during the pre-index period. Observed TDD will be calculated during both the entire pre-index and post-index periods.
- ❖ Adherence will not be included as a covariate here due to the high collinearity between time and adherence.

Exploratory Analysis: Mediator Effect of Adherence (PDC) and Observed Total Daily Dose (TDD) on Insulin-related Pharmacy Costs

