Mediation analysis following the below modeling steps will be considered to understand the impact of index event (time: pre-index indicates use of other non-U-500R insulins and post-index indicates exposure to U-500R use) on insulin-related out-of-pocket costs through potential mediators. Adherence (measured by PDC) and Observed Total Daily Dose (TDD) are considered as potential mediators between costs and treatment period (i.e. exposure). The key steps in mediation analysis include a model of the outcome (costs) as a function of both the mediators (PDC, and TDD) and the predictor (treatment period) and a model of the mediators (PDC and TDD) as functions of the predictor (treatment period). Confounders will be included in the models. Unfortunately, certain confounding variables are unobserved in claims data, e.g., weight, HbA1c.

- 1.) Suppose the dataset consists of n patients. For patient i ($i = 1, \dots, n$), denote by Y_{ik} the outcome variable of interest, e.g. costs, during the period k ($k = 0, 1$), where $k = 0$ refers to pre-index period and $k = 1$ refers to the post-index period.
- 2.) Let M_{ijk} be the mediators at period k , and $j=1,2$ denotes the different mediators PDC and TDD
- 3.) Let A_{ik} be a binary indicator of treatment during period k . Write $\mathbf{A}_i = \{A_{ik}\}_k$. According to the design, all the patients did not take the U-500R during the pre-index period, but they took the U-500R during the post-index period, thus $A_{ik} = k$ for $k = 0, 1$.
- 4.) A set of covariates as potential confounding variables, including age, sex, region, pre-index CCI score.

$$Y_{ik} = \beta_0 + \beta_A A_{ik} + \beta_{M1} M_{i1k} + \beta_1 \text{Age} + \beta_2 \text{Sex} + \beta_3 \text{Region} + \beta_4 \text{CCI} + \beta_5 M_{i1k} + \beta_6 M_{i2k} + d_i + \varepsilon_{ik}$$

$$M_{ijk} = \alpha_0 + \alpha_{Aj} A_{ik} + \alpha_{1j} \text{Age} + \alpha_{2j} \text{Sex} + \alpha_{3j} \text{Region} + \alpha_{4j} \text{CCI} + b_{0i} + b_{Mij} + b_{Ai} A_{ik} + \eta_{ijk},$$

where random errors ε_{ik} and η_{ijk} along with random effects d_i , b_{0i} and b_{Ai} are mutually independent over i, j, k . The random effects b_{i0} and b_{iA} capture the dependence among M_{ijk} 's. The random effects d_i 's, control the dependence between the outcome variable between the pre-index and post-index periods given the mediators and confounders,

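### The printed cost-mediation equations enter PDC twice and give PDC and TDD one shared intercept, which on raw scales can bias the indirect effects

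*Protocol*

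**What the plan says.** The model is in Protocol section 6.4.1, under the exploratory analysis of the mediator effect of adherence and TDD on insulin-related pharmacy costs. Exploratory Objective 3 in section 4.1 asks for it in all three cohorts (Kwikpen, syringe, any U-500R). Its key steps are a cost model in both mediators and period, and "a model of the mediators (PDC and TDD) as functions of the predictor (treatment period").

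- The index j "denotes the different mediators PDC and TDD", so `M_i1k` is PDC and `M_i2k` is TDD in period k. Exposure `A_ik` equals k: 0 before and 1 after initiation.
- The cost equation contains "\beta_{M1} M_{i1k} + \beta_1 \text{Age" and, later in the same line, "\beta_5 M_{i1k} + \beta_6 M_{i2k} + d_i". PDC therefore has two coefficients, `beta_M1` and `beta_5`. TDD has one, `beta_6`.
- The mediator equation begins "M_{ijk} = \alpha_0 + \alpha_{Aj} A_{ik". The period and covariate coefficients carry the mediator index j; the intercept does not.
- Its random part is "b_{0i} + b_{Mij} + b_{Ai} A_{ik} + \eta_{ijk". The effects `b_0i` and `b_Ai` are common to both mediators, and `b_Mij` is specific to each. The text says that the common effects "capture the dependence among" the mediators. It neither describes `b_Mij` nor lists it among the independent terms.
- The covariates are age, sex, region and pre-index CCI. The main cost model in the same section also has Medicare status, uses a log link, and carries the note "Adherence will not be included as a covariate here due to the high collinearity between time and adherence".

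The fitted coefficients then go into a counterfactual decomposition with parametric bootstrap intervals.

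**The concern.** The indirect effect through each mediator is built from two coefficients: the effect of period on the mediator (`alpha_Aj`) and the effect of the mediator on cost. The printed equations disturb both. The cost equation offers two coefficients for PDC where one is needed. The mediator equation makes PDC and TDD equal the same number for a pre-index patient at the reference level of every covariate, although one is a proportion and the other exceeds 180 units/day in both periods by the selection criteria. A patient's shared shift `b_0i` likewise moves both by the same raw amount. Results would then change with arbitrary choices, such as coding PDC as a proportion or a percentage, or centring age.

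At stake is the planned account of the cost result: how much of any change comes from a different copay burden, and how much from purchasing more insulin or covering more days.

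**Working it through.** The protocol gives no figure for this analysis, so there is none to reproduce. The check takes the printed equations as they stand.

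**Cost equation.** Fixed-effect columns: intercept 1, period 1, PDC 1, age 1, sex 1, region 3 (four regions), CCI 1, PDC again 1, TDD 1, which makes 11. Two columns are identical, so the rank is 10. Pooled least squares (without `d_i`) on simulated data gave:

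- as printed, minimum-norm solution: `beta_M1` + `beta_5` = 337.1 + 337.1 = 674.2, `beta_A` = -136.5, `beta_6` = 0.964;
- with one PDC term: 674.2, -136.5, 0.964.

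The sum and all other coefficients are unaffected by the duplicate.

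**Mediator equation.** Assumed inputs, not from the protocol: 600 patients, PDC about 0.64 before and 0.10 higher after, TDD about 256 before and 50 higher after, with within-patient correlation. The simulated sample had mean changes of 0.114 and 52.9. Maximum-likelihood estimates on raw scales were:

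| Fit | PDC period effect | TDD period effect |
|---|---|---|
| Sample mean change | 0.114 | 52.9 |
| As printed, variances common to both mediators | -3.76 | 56.8 |
| As printed, variances by mediator | 0.114 | 57.8 |
| `b_Mij` left out, common variances | -32.2 | 85.2 |
| `b_Mij` left out, variances by mediator | 0.114 | 117.6 |
| Own intercept `alpha_0j`, either variance structure | 0.114 | 52.9 |

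The mechanism is visible in the intercepts. Fitted separately they are 0.60 and 241.4. Under common variances the shared intercept is their average, (0.60 + 241.44)/2 = 121.0. With variances by mediator it settles at 0.60, and the TDD level has to be made up by the period effect, the covariates and an inflated variance of `b_Mij` for TDD (11,218 against 2,404).

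**Indirect effects on the same inputs** (product of coefficients, in cost units):

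- via PDC, own intercept: 674.2 x 0.114 = about 77;
- via PDC, as printed with common variances: 674.2 x (-3.76) = about -2,540 (from unrounded values);
- via TDD, own intercept: 0.964 x 52.9 = about 51;
- via TDD, as printed with variances by mediator: 0.964 x 57.8 = about 56, since 57.8/52.9 = 1.09.

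**Scaling.** With both mediators standardised, the equation as printed gives 0.652 and 0.763 against sample values of 0.648 and 0.767.

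**Second data set.** A separately simulated set, also on assumed inputs, showed the same pattern. The PDC change was -7.3 against +0.10 with common variances, and the TDD change was about 15% too high with variances by mediator. Mediator-specific intercepts recovered both.

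**The case against.** The strongest defence is that these are drafting slips. Every other fixed coefficient in the mediator equation carries j, so the bare intercept may be a lost subscript. The prose describes the intended cost model correctly, as a function of PDC, TDD and period, and software that drops one aliased PDC column would fit it. The equations were read from a PDF, so the printed original should be checked. Scaling and variance structure may be settled in an SAP that is not at hand, and the protocol says only that this modelling will be considered. All of that limits the severity. It does not make the printed equations right, and a programmer who follows them literally can get wrong indirect effects.

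A reader might infer more than the document supports:

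- *That the model cannot yield the decomposition.* It can: the sum of the two PDC coefficients and all the others remain estimable, and on standardised scales the shared intercept does little harm.
- *That PDC and TDD have only the same random effects, so their correlation is non-negative and bounded by the ratio of their standard deviations.* The equation also prints `b_Mij`, indexed by mediator. Its covariance across mediators is not stated, so no such bound follows. Nor does the protocol give a TDD standard deviation for this cohort; the values in its rationale come from a broader group, before the cut at 180 units/day.
- *That the mediator covariance biases the indirect effects directly.* In a linear model without interactions these are products of coefficients. The covariance bears on estimation and on the intervals.
- *That leaving adherence out of the main cost model for collinearity contradicts using it here, or that the two models must share a link.* A mediator has to enter the mediation model and is expected to correlate with exposure. An additive model gives a simple decomposition. Both are choices that need a reason, not errors.

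On Medicare, the defence is partly right. Every patient contributes both periods, so a pre-index covariate cannot confound the effect of period on the mediators. It may still confound the relation between mediators and cost, and the protocol already uses it for the same outcome.

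**Conclusion.** The point holds as a specification error in an exploratory analysis. PDC is entered twice, which leaves its separate coefficients unidentified but is harmless to their sum. The shared intercept is the more serious fault, because on raw scales it can distort the period effects on the mediators. The common unscaled random effects and the undefined `b_Mij` add ambiguity: in the simulation, leaving `b_Mij` out more than doubled the TDD effect with variances by mediator (117.6 against 52.9).

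The size cannot be fixed from the protocol. On assumed inputs it ran from negligible (standardised mediators), through 9% to 15% on the TDD effect (variances by mediator), to an impossible negative change in a proportion (common variances). It also depends on covariate coding: a full set of sex or region indicators for each mediator would absorb the missing intercept. The magnitudes rest on single simulated data sets and illustrate the fault; they do not predict the study's result. The primary and secondary objectives are untouched.

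**What to change.** Check the original equations for the duplicate term and the missing subscript, then rewrite both before programming:

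1. Cost equation: one term for PDC and one for TDD.
2. Mediator equation: an intercept for each mediator, `alpha_0j`.
3. Define `b_Mij`. Use mediator-specific random effects and residual variances with a free covariance between PDC and TDD, or standardise the mediators, and state the scale of PDC.
4. Add Medicare status to the covariates, as in the main cost model.
5. Give one sentence each on why the link differs from the main cost model and on how the stated collinearity of PDC with time will be handled.

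The cost is two rewritten equations and a few lines of text. No new data are needed.

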Out-of-pocket costs	Truven: Inpatient service table, outpatient service table, outpatient pharmacy claims table	
Out-of-pocket pharmacy costs will be computed among T2DM patients before and after high-dose U-500R syringe initiation, high-dose U-500R Kwikpen initiation, and any high-dose U-500R initiation.
 
Out-of-pocket pharmacy costs will be further classified into:
 
 • Diabetes-related out-of-pocket pharmacy costs (i.e., the costs associated with any insulins and AHAs [sulfonylureas, TZD, biguanides, meglitinides, alpha-glucosidase inhibitors, DPP-4 inhibitors, SGLT-2, bile acid sequestrant, fixed-dose combination, GLP-1, pramlintide) • Insulin-related out-of-pocket pharmacy costs • All-cause out-of-pocket pharmacy costs (i.e., all the pharmacy costs in the 12 months period) 
Costs will be adjusted to 2018 US dollars using the annual medical care and drug costs components of the Consumer Price Index (CPI) to reflect inflation.

Note: Treatment pattern in the Truven database will be conducted using the 12-month pre- and post-index period.

[2019-8636] Observational Study Protocol

6. Sample Size and Statistical Methods**6.1 Determination of Sample Size**

The preliminary sample sizes for the VHA databases from 2013–2018 are shown below. This study will use the most recent 5 years of data available.

Table 3. Preliminary Sample Size

Database	Counts
VHA (01APRIL2013–31MARCH2018)	
Kwikpen:	
Evidence of U-500R Kwikpen during the identification period	2,596
Evidence of T2DM	2,536
≥1 HbA1c in the pre-index and post-index periods	741
After applying other inclusion/exclusion criteria and excluding patients with pump use along with U-500R Kwikpen	647
Syringe Use:	
Evidence of U-500R syringe use during the identification period	5,162
Evidence of T2DM	4,956
≥1 HbA1c in the pre-index and post-index periods	1,930
After applying other inclusion/exclusion criteria and excluding patients with pump use along with U-500R syringe	1,766

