Mediation analysis is a collection of methodologies designed to formalize and quantify possible mechanisms (i.e., causal pathways) linking a cause to an effect^{35,36}. The total effect of an exposure on an outcome is decomposed into direct (blue thick arrow) and indirect effects (red arrows) through mediators. Causal mediation analysis further defines both direct and indirect effects based on counterfactual models and is able to provide a causal interpretation. Causal mediation analysis is becoming an important tool for investigating pathways or mechanisms that explains the treatment effect and the underlying mechanism in epidemiology and in the social sciences.

In contrast to non-U-500R insulin therapies that are mostly basal-bolus regimen that requires more than one insulin use at a time, U-500R is an insulin-monotherapy. It is expected that, if the insulin requirement of patients and their adherence behavior were to remain the same, the out-of-pocket costs for purchasing insulins would be lower for the period when patients were exposed to U-500R treatment than for the period when patients are exposed to other insulins. However, from a previous study, it is observed that the observed total daily dose and PDC were different before and after patients were exposed to U-500R. While patients' underlying insulin requirement may or may not have changed, the changes in the observed total daily dose using claims data may reflect more of the compliance behavior (i.e. using the right amount of insulin). Similarly, PDC, another aspect of treatment compliance, may change due to the different insulin treatment characteristics. Changes in obtained insulins quantity (reflected in TDD) as well as changes in number of days with insulins (reflected in PDC) will impact number of insulin purchases (i.e. number of claims filed) and therefore the amount of out-of-pocket costs. As a result, the observed insulin-related out-of-pocket costs may be impacted by the change in the copay needed (direct effect of the exposure to different insulins) as well as the changes in TDD and PDC (indirect effect of the exposure to different insulins)

[2019-8636] Observational Study Protocol

Confounder
(age, gender, CCI, weight, HbA1c, etc.)

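### The mediation model's direct effect is a pre/post cost difference, not an identified U-500R copay effect, because exposure and period are the same variable

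*Protocol*

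**What the plan says.** Exploratory Objective 3 is analysed in the Truven data, with a 12-month window on each side of the index date.

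- **Cost regression (Section 6.4.1, Research Objective 3, Multivariate Analysis).** A log-link mixed model is used to study "factors associated with insulin-related out-of-pocket pharmacy costs in the pre-and post-index periods". The covariate list is described as complete. Its time-varying terms are the pre/post indicator and insulin dose: "Observed TDD will be designated as the time-varying covariate in the model (measured both before and after the index date"). The rest are baseline values: "Age, sex, region, Medicare (yes/no), and CCI score will be assessed during the pre-index period".
- **Mediation model (same section, Mediator Effect).** Exposure is defined through time: "time: pre-index indicates use of other non-U-500R insulins and post-index indicates exposure to U-500R use". The formal coding is A_ik = k, because "all the patients did not take the U-500R during the pre-index period, but they took the U-500R during the post-index period". PDC and TDD are the mediators. The listed confounders are age, sex, region and pre-index CCI; Medicare is not among them.
- **Interpretation.** The text attributes part of the cost difference to the "change in the copay needed (direct effect of the exposure to different insulins") and the rest to changes in TDD and PDC. It presents causal mediation analysis as able to support a causal reading.
- **Costs available (Section 5.5, Table 2).** Insulin-related and diabetes-related costs are defined, and also "All-cause out-of-pocket pharmacy costs (i.e., all the pharmacy costs in the 12 months period"). Only the insulin-related cost enters the two models.

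**The concern.** With one pre/post variable acting as both calendar and treatment, the model cannot tell a change of insulin from anything else that altered the patient's cost share between the two years. The hypothesis in Section 3 is that one copay in place of several lowers what the patient pays. A general shift in cost-sharing over the same year could look like that saving or hide it. The risk is greatest in the mediation analysis, where the remaining period coefficient is given a mechanism (copay) and a causal vocabulary. If the Section 4.1 question of what costs would have been at an unchanged dose is answered from these models, the answer carries the same coefficient.

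**Working it through.** The Protocol states no effect size, SD or Truven sample size for costs, so there is no planned figure to reproduce. The check is algebraic.

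**1. Identification in the mediation model.** Take the outcome equation of Section 6.4.1 with each mediator entered once and subtract the pre-index from the post-index value for patient i. Age, sex, region, CCI and the patient effect d_i cancel:

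Y_i1 − Y_i0 = β_A + β_5·ΔPDC_i + β_6·ΔTDD_i + error.

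Now let every patient's cost also shift by an average amount s for reasons unrelated to insulin. The intercept becomes β_A + s, and only this sum can be estimated. A numerical check on an artificial data set agrees. The columns intercept, exposure, age, sex, CCI, PDC and TDD have rank 7 of 7. Adding a separate period column gives 8 columns and still rank 7.

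**2. Calendar time.** The two windows are adjacent 12-month blocks, so calendar time advances by exactly one year for every patient. Within patients a linear calendar term is therefore another constant, collinear with exposure (rank 1 of 2). Index dates differ between patients, but that allows only a between-patient adjustment, and none is planned.

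**3. What the existing safeguards remove.**
- Adjustment to 2018 dollars (Table 2) removes an average price index, not a change in a patient's own cost share.
- Twelve-month windows (Sections 3 and 5.1) put a full deductible cycle on each side, but do not hold the deductible or copay tier equal across the two.
- Continuous enrolment (Section 5.3.1) prevents gaps in coverage. Section 5.2 says that these data follow patients across health plans, so it need not mean the same plan.
- Medicare status is fixed at its pre-index value in the regression and is not listed in the mediation model, so entry after index is not represented.

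**4. Size under the log link.** Let θ be the true U-500R cost ratio and g the shared ratio. The pre/post ratio estimates θ × g:

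| θ | g | θ × g |
|---|---|---|
| 0.90 | 1.10 | 0.99 |
| 1.00 | 0.90 | 0.90 |
| 1.00 | 1.10 | 1.10 |

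The values of θ and g are illustrations; the multiplication itself needs no assumed sample size or SD. In the mediation equation, which is linear in cost, the bias is the additive s of step 1.

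**5. What a control cost would do.** All-cause minus diabetes-related cost gives a non-diabetes pharmacy cost for each patient and period. If it changes by the ratio h, the contrast of the two changes estimates θ × g / h. With h = g it returns θ: 0.90 × 1.10 / 1.10 = 0.90. With h = 1.00 it returns 0.99 and corrects nothing. A model with cost type, time and their product has full rank (4 of 4).

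**6. Price in precision.** If the two log changes have equal variance and correlation r, the SD of their difference is √(2 − 2r) times that of one: √2 = 1.41 at r = 0 and √1.4 = 1.18 at r = 0.3.

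**The case against.** The strongest reply is that this is an openly stated feature of the design. Every outcome in the study is an uncontrolled pre/post comparison, Objective 3 is labelled exploratory, the mediation analysis is only to be considered, and sensitivity models can be left to an SAP. This keeps the point moderate. It does not remove it, because the Protocol itself fixes the coding, a covariate list it calls complete, and the copay interpretation.

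The shared drift would also be partly visible: all-cause and diabetes-related costs are to be described in both periods, and their means can be subtracted. That stands, but no contrast with an interval is planned, and all-cause cost on its own includes insulin. It also stands that individual plan changes matter only through their average net effect. The mediation text does admit unobserved confounders, but its examples are weight and HbA1c, not change over time.

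A reader might infer four stronger things that the document does not support:
- **That any cost change is credited to U-500R.** Too broad: inflation adjustment, full-year windows and the enrolment rule each remove something.
- **That both models claim a copay effect.** Only the mediation text does; the regression is described as a study of associated factors.
- **That a false-positive rate can be stated.** The Protocol gives no Truven sample size, SD of cost change or size of drift. Table 3 counts are for VHA, which supplies no cost analysis, so no rejection rate is offered here.
- **That non-diabetes cost cleanly isolates the effect.** Under a shared deductible or cap, insulin spending alters what the patient pays for other drugs, and the use of those drugs may itself change.

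**Conclusion.** The point holds in a limited form and should be addressed. As written, the mediation direct effect is the pre/post difference in insulin cost at given PDC and TDD. It equals a U-500R copay effect only if average cost-sharing, after inflation adjustment, was otherwise the same in the two years, and nothing in the plan examines that assumption. The bias is one for one: multiplicative under the log link, additive in the linear equation. Its direction and actual size cannot be derived from the Protocol. For the cost regression the same limit applies, but the association wording already claims less.

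**What to change.** 1. State in Section 6.4.1 that the time coefficient and the mediation direct effect are pre/post differences at given TDD (and, for mediation, PDC), not an identified U-500R copay effect. Name average change in cost-sharing between the windows as an uncontrolled alternative explanation.
2. Keep the planned models and add one prespecified sensitivity analysis. Derive non-diabetes out-of-pocket pharmacy cost (all-cause minus diabetes-related) per patient and period. Fit a log-link mixed model to the stacked insulin and non-diabetes costs with cost type, time, cost type × time and TDD × cost type, so that the insulin dose coefficient is not imposed on non-diabetes cost. Fix a rule for zero costs.
3. Report the cost type × time ratio with its confidence interval beside the raw pre/post ratio. Treat it as supportive; it should not act as a gate on the main result.

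The cost is wording and one model on costs already in Table 2, with no new data or patients. The interval for the contrast would be about 1.2 to 1.4 times as wide under the assumptions of step 6. The control is imperfect for the reasons given under the objection, and insulin-specific formulary changes would remain in the estimate.

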U-500 regular insulin (U-500R) is a five-fold concentrated form of insulin (contains 500 units of insulin per mL) indicated to improve glycemic control in adults and children with diabetes mellitus requiring more than 200 units of insulin per day. It was first approved in 1994 by the United States Food and Drug Administration (FDA).^{12,13} To avoid dosing errors, it is currently available for administration through pens and vials with the dedicated U-500R syringe.¹⁴ U-500R has unique prandial/basal actions¹⁵ and thus can be used as insulin monotherapy. However, the safety and efficacy of U-500R used in combination with other insulins has not yet been determined. Also, the safety and efficacy of U-500R delivered by continuous subcutaneous infusion is been determined in a recent clinical study.¹⁶ An open-label trial evaluated transitioning from high-dose U-100 to U-500R and demonstrated that similar reduction in A1c could be achieved with twice or thrice-daily regimens of U-500R, which mitigate physical discomfort and potential barriers to adherence associated with U-100.¹¹ Measures of disease burden were reduced with both regimens while the compliance domain improved in patients receiving U-500R.¹⁷ In the real-world setting, U-500R (vial) has been shown to improve glycated hemoglobin (HbA1c) levels among patients with T2DM, **Error! Bookmark not defined.** and is associated with lower health care costs and better adherence than U-100 users prescribed a similar dose.^{17,18} A recent real-world study found that, U-500R Kwikpen initiation was associated with a clinically significant drop (~0.7% drop) in HbA1c accompanied by an average increase of 0.21 hypoglycemic event per year after adjusting for age, gender, race, BMI, CCI score, and TDD.¹⁹ The insulin dose increased more than 80 units/day on

[2019-8636] Observational Study Protocol

average after U-500R Kwikpen initiation and the medication adherence as measured by PDC improved.¹⁹

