Once the coefficient estimates from the models fitting are obtained, the mediation effects will be estimated following standard decomposition approach using counterfactual framework. The confidence intervals will be provided by using parametric bootstrap approach.

[2019-8636] Observational Study Protocol**7. Safety Evaluations****7.1. Adverse Events**

This is a non-interventional study based on secondary data use, and therefore no ICSR reporting is required. The study protocol-defined adverse events (AEs) include hypoglycaemia. Hypoglycemia events in the pre-index and post-index period will be evaluated using the ICD-9 codes from the Ginde algorithm (Appendix 1). All protocol-defined adverse events collected will be summarized in the final study report. No other AEs will be collected.

[2019-8636] Observational Study Protocol**8. Subject Consent to Release Information, Ethical Review, and Regulatory Considerations****8.1. Subject Consent to Release Information**

As this is an observational study that uses data previously collected and does not impose any form of intervention, the data has been de-identified to protect subject privacy. Therefore, a formal Consent to Release Information form is not required.

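### The mediation intervals rest on a linear cost model that differs from the protocol's own log-link cost model, and the dose-mediated interval is likely too narrow if cost spread rises with dose

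*Protocol*

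**What the plan says.** All three statements are in Protocol section 6.4.1, under Exploratory Objective 3.

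- **Main cost analysis (Multivariate Analysis).** "A generalized linear mixed model (details above) with log link will be used to evaluate factors associated with insulin-related out-of-pocket pharmacy costs". No distribution family is named.
- **Mediation model (Exploratory Analysis: Mediator Effect).** Y is "the outcome variable of interest, e.g. costs, during the period k". The equation sets untransformed Y equal to a sum of treatment period, PDC, TDD, covariates, one patient random intercept and one residual. There is no link and no variance function. On the errors and random effects it says only that they "are mutually independent over i, j, k".
- **Estimation and intervals (end of the same subsection).** "Once the coefficient estimates from the models fitting are obtained, the mediation effects will be estimated following standard decomposition approach using counterfactual framework". Then: "The confidence intervals will be provided by using parametric bootstrap approach".

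The protocol also says why dose should matter for cost: changes in TDD and PDC "will impact number of insulin purchases (i.e. number of claims filed) and therefore the amount of out-of-pocket costs".

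**The concern.** A parametric bootstrap simulates from the fitted model, so it can show only the variability which that model allows. If the spread of costs grows with the amount of insulin bought, patients with high TDD have both the most leverage on the TDD slope and the noisiest costs. A model with one common residual variance then understates the uncertainty of that slope. The TDD-mediated effect is essentially the mean TDD change multiplied by that slope, so its interval is too short.

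At stake is how precisely the study reports the part of the cost change that runs through dose. The protocol itself treats cost on a multiplicative scale a page earlier, so the linear equation is not an obvious deliberate choice.

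**Working it through.** **1. No figure to reproduce.** The protocol gives no power, sample size or interval width for this analysis. Table 3 has VHA counts only, and costs come from Truven. The question can only be examined by simulation over assumed inputs.

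**2. Is TDD likely to be right-skewed?** Section 3 gives TDD of 198 ± 78 (median 189) for syringe and 188 ± 72 (median 176) for Kwikpen initiators, before any dose restriction. Section 5.3.1 then requires TDD above 180 in both periods, with a ceiling only at 2000. Assume a lognormal shape:
- Log-variance = ln(1 + (SD/mean)²): ln(1 + (78/198)²) = 0.144 and ln(1 + (72/188)²) = 0.137.
- Implied medians are 184 and 176, close to the stated values.
- The cut at 180 keeps about 52% and 47% of patients.
- Skewness after the cut is about 1.8 in both.

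**3. Simulation with log-link costs.** Assumptions:
- Two periods, with a TDD rise of 80 units/day. This is taken from the earlier Kwikpen study in section 3 ("The insulin dose increased more than 80 units/day on" average).
- Gamma costs, conditional CV 0.8, patient SD 0.4 on the log scale, and n = 100, 300 and 600.
- The linear random-intercept cost model was fitted with PDC entered once, because the printed equation lists it twice.
- Dose-mediated effect = mean TDD change × TDD slope.
- The parametric bootstrap used Gaussian errors with constant variance.

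Coverage refers to the value that the linear estimator targets.

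| Scenario | Bootstrap SD ÷ true SD | Coverage of nominal 95% |
|---|---|---|
| Linear truth, constant variance (code check) | 1.00–1.04 | 93.5–95.7% |
| Log slope 0 per 100 units | 1.06–1.12 | 94.5–95.5% |
| Log slope 0.05 (n = 300) | 1.01 | 94.5% |
| Log slope 0.1 | 0.88–0.91 | about 91% |
| Log slope 0.2 | 0.69–0.71 | 82–83% |
| Log slope 0.3 | 0.50–0.54 | 67–75% |
| Log slope 0.2, symmetric TDD | 0.96–0.99 | 93.5–94% |
| Variance falling with dose (n = 300) | 1.15 | 96% |

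The ratio and the coverage agree: for an unbiased normal estimator, coverage = 2Φ(1.96 × ratio) − 1. A ratio of 0.70 gives about 83%. A larger n does not help, because the ratio stays near 0.70 at slope 0.2 for all three sample sizes.

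**4. Simulation on the elasticity scale.** These runs used gamma costs and model-based intervals of the same linear model. With TDD truncated at 180 and n = 300, coverage was about 96% with no dose–cost relation, 90–93% at elasticity 0.3, 88–90% at 0.6 and 78–79% with proportional costs. Further runs at n = 200 and 400 gave 93–94% at elasticity 0.3, 89–90% at 0.6 and 81–85% with proportional costs. A separate set with costs proportional to TDD × PDC (CV 0.4–0.7, n = 200–400) gave 84–89%. In that set the direct and PDC-mediated intervals were little affected (93–96%).

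**5. Effect of resampling patients, same linear estimator.**
- Slope 0.2, n = 300: mean width rises from 68 to 90 dollars (90.4/68.0 = 1.33) and coverage from 83% to 91%.
- Slope 0.2, n = 600: width rises from 47 to 63 dollars and coverage from 82% to 93%.
- Proportional costs, n = 300: coverage rises from 78–79% to about 90%.

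Resampling does not repair the mean form. At slope 0.2 the linear estimate tends to about 74 dollars against a true dose-mediated effect of about 65 (73.8/65.3 = 1.13).

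**The case against.** The strongest reply is that the documents do not establish narrow intervals. The quoted error statement concerns independence, not variance. A log link fixes the mean and says nothing about spread, and no family is named. The table above includes settings where the interval is right (little or no slope, or symmetric TDD) and one where it is too wide. Out-of-pocket costs also pass through copays and deductibles, so strict proportionality to dose is an assumption. All of this stands, and it is why the point is conditional.

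Three stronger readings are tempting and are not supported:

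- *The interval is too narrow as a matter of fact.* This needs cost variance rising with level, skewed TDD and an appreciable slope. Only the direction of the dose–cost relation and the entry limit that favours skew are in the protocol.
- *A dose-mediated effect could be declared where none exists.* With no dose–cost relation, coverage was about 94.5–96%.
- *The bootstrap is at fault whatever the cost model.* With a log-link model and a suitable variance family, a parametric bootstrap would simulate the right spread. The root is the outcome equation.

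Nor does the protocol single out the dose-mediated effect as the main mediation result. Its stated expectation, lower cost at unchanged requirement and adherence, is about the direct effect.

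One might add that error distributions and resampling details belong in an SAP. That does not dispose of the point: the cost equation and the interval method are both written into the protocol, and the equation differs from the protocol's other cost model.

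**Conclusion.** The point holds in conditional form. The protocol uses two different models for the same costs and takes the mediation intervals from the one less suited to skewed, dose-dependent spending. If cost spread rises with cost level and cost rises appreciably with TDD, the nominal 95% interval for the TDD-mediated effect probably covers about 90–93% for a weak relation and 78–89% for near-proportional costs. Steeper log-linear relations do worse. These figures rest on assumed gamma costs, assumed CVs and slopes, and assumed sample sizes. They show a range, not this study's actual error.

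The harm is overstated precision of a dose-mediated effect that is really there. Severity is minor: the analysis is exploratory, and the protocol says only that its modelling steps will be considered.

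**What to change.** Make two changes together in section 6.4.1:

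1. In the counterfactual decomposition, replace the linear cost equation with the log-link mixed model already planned for Objective 3, and state its distribution family.
2. Replace the parametric bootstrap with a patient-level bootstrap. Resample patients, keep both periods and both mediators together, refit all equations on each draw, use at least 2,000 draws, and report percentile or BCa intervals for the direct, PDC-mediated and TDD-mediated effects.

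The first change addresses the mean form and, with a suitable family, most of the variance problem. The second protects against whatever misfit remains, in either direction. The simulations tested the second change alone, not the pair.

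The cost is a few sentences of text and more computing. The dose-mediated interval will probably be wider, and coverage should improve but may stay slightly below 95%.
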